### **3.3.3. Completion of a Patient's Participation in the Study and Overall Study Completion**

#### **3.3.3.1. Completion of a Patient's Participation in the Study**

The length of a patient's participation in the study will be from the time the informed consent form is signed through the Week 52 visit. A patient will be considered to have completed the study when they have completed the Week 52 assessments. Patients who do not participate in the open-label extension study will be considered to have completed the study after they complete the safety follow-up.

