### 5.2.5. Treatment Discontinuation

A patient's study treatment may be discontinued at any time at the patient's/parent/legal guardian's request or at the discretion of the Investigator, Medical Monitor or Sponsor. The following may be justifiable reasons for the Investigator, Medical Monitor or Sponsor to discontinue a patient from treatment:

- The patient experiences an intolerable or unacceptable AE
- The patient is unable to comply with the requirements of the protocol
- The patient participates in another investigational study without the written authorization of the Sponsor

Discontinuation of treatment does not imply withdrawal from the study.

Patients who discontinue treatment prematurely will be asked to complete the early termination visit prior to their last dose of study drug as noted in the SOA in [Appendix 1](#).

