#### 7.1.3. Adverse Events Occurring Following Patient Discontinuation of Treatment

For patients who prematurely discontinue study treatment (see [Section 5.2.5](#)), but who are not withdrawn from the study, AEs will continue to be recorded until the patient completes the study (see [Section 3.3.3.1](#) for definition of patient completion). See [Section 7.6](#) for reporting requirements after the patient completes the study.

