### 9.3. Analysis Sets

The following are the analysis populations for this study:

**Randomized Population:** The Randomized Population consists of all patients who are randomized into the study.

**Note:** If a randomized patient has a sibling assigned to the same treatment group, the non-randomized sibling (i.e., the sibling assigned to the same treatment as the randomized sibling) will not be included in the randomized population (see [Section 5.5.1](#)).

**Safety Population:** The Safety Population will consist of all patients who receive at least 1 dose of study drug. This will include the set of patients who were assigned the same treatment as their randomized sibling.

**Full Analysis Population:** The Full Analysis Population for efficacy analyses will be a modified intent to treat (mITT) population and will consist of all patients in the Randomized Population who receive at least 1 dose of study drug, and provide at least 1 valid post Baseline NSAA efficacy assessment.

**Per Protocol Population:** The Per Protocol (PP) Population will consist of all patients in the Full Analysis Population who complete the study, without any significant protocol violations.

PK Population: The PK Population will consist of all patients in the Safety Population who receive at least 1 dose of edasalonexent and have at least 1 measured plasma concentration.

Other analysis populations may be defined in the SAP.

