3. PATIENT POPULATIONS

3.1. Population Definitions

The following patient populations will be evaluated and used for presentation and analysis of the data:

- Randomized Population: all patients who are randomized into the study with patients to be analyzed based on the study treatment they were randomized to.
- Safety Population: all patients who receive at least one dose of study drug with patients to be analyzed based on the actual study treatment received.
- Full Analysis Population (FAP): all patients in the Randomized Population who receive at least one dose of study drug and provide at least one non-missing post-Baseline NSAA efficacy assessment.
 - Note that the FAP will exclude patients on eteplirsen at randomization and patients will be analyzed based on the study treatment they were randomized to.
- Per Protocol (PP) Population: all patients in the FAP who complete the 52-week treatment period of the study without any significant protocol deviations with patients to be analyzed based on the study treatment they were randomized to.

The set of patients in the Per Protocol population may be updated due to study drug compliance information which will not be collected until after database lock and unblinding due to the COVID-19 pandemic, see [Section 3.2](#).

note: the variable to determine a patient completing the 52-week treatment period is from the End of Study eCRF page “Did subject complete the study?” = Yes.

The FAP will be the primary population for the analysis of efficacy parameters. The Safety Population is the primary population for the analysis of safety endpoints.

Note that if siblings are enrolled, only one sibling will be included in the Randomized Population. This is to avoid having siblings being randomized to different study medications, increasing the risk a subject will inadvertently take incorrect study medication. The second sibling will be assigned to the same treatment group as the randomized sibling. If both siblings meet the inclusion/exclusion criteria, the sibling to be included in the Randomized Population will be the first sibling randomized, both siblings will be included in the Safety Population (see [Section 3.1](#)). The sibling not included in the Randomized Population will have their data presented in the listings and will be included in some of the sensitivity analyses.

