4.9. Treatment Exposure and Compliance

Throughout the study, patients and their parents/caregivers will complete a diary documenting study drug administration and diet compliance. For the Safety Population, treatment duration, number of administrations, and compliance (summarized by assessing capsule count) will be summarized by treatment group and overall.

Treatment Duration: Treatment Duration will be the number of days from the patient's first dose until their Week 52 visit. If the patient discontinued from the study and did not have a Week 52 visit the subject's Early Termination visit will be used (note: if the subject does not have an early termination visit, the last visit will be used).

The patient's date of first dose is determined by the study drug administration at baseline:

- If for the baseline visit the "first dose of the day administered in clinic" = "No" (i.e., variable EX.EXPERF= "N") then the date of first dose is the date in the field EX.EXSTDAT (i.e., the "Date of study drug administration").
- Otherwise the date of first dose is the date of the baseline visit.

Expected Average Daily Dose: The expected number of capsules that a patient is to take each day is specified at each visit that the patient receives new study medication (e.g., Baseline, Week 13, Week 26, and Week 39, but there may be distribution at unscheduled visits as well). The daily total of capsules is broken up into morning/afternoon/evening administration. The exact capsule count per dose and the capsule dose strength (i.e., 250 mg or 100 mg) will be provided through the IXRS based on the patient weight at each study visit.

The periods are:

- 1st day patient takes study medication to the day before the Week 13 visit
- Week 13 to the day before the Week 26 visit
- Week 26 to the day before the Week 39 visit

- Week 39 to the day of the Week 52 visit.

Please note the following potential modifications to these periods:

- If the patient discontinues the study early, the corresponding period will end at the date of the early termination visit.
- If the patient has an unscheduled visit where study drug is dispensed the periods will be updated to account for this visit. The following is an example of the update to the algorithm where the patient had an unscheduled visit between the Week 26 and Week 39 visits.
 - 1st day patient takes study medication to the day before the Week 13 visit
 - Week 13 to the day before the Week 26 visit

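### SAP 4.9 ends treatment duration at the Week 52 visit, so for a boy who stops drug but stays in the study, time off drug is counted as treatment

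*SAP*

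**What the plan says.** **Treatment duration.** SAP 4.9 runs it from "first dose until their Week 52 visit". The exception opens with "If the patient discontinued from the study and did not have a Week 52 visit"; the Early Termination visit is then used or, failing that, the last visit. Both conditions refer to the study and its visits. Stopping drug does not trigger the exception.

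**Stopping drug and staying.** Protocol 5.2.5 states "Discontinuation of treatment does not imply withdrawal from the study". Protocol 7.1.3 provides for boys who stop early "but who are not withdrawn from the study, AEs will continue to be recorded until the patient completes the study".

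**Study completion.** Protocol 3.3.3.1 states "A patient will be considered to have completed the study when they have completed the Week 52 assessments". For boys who do not enter the extension it adds the safety follow-up. Neither condition requires being on drug.

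**Per Protocol Population.** Protocol 9.3 takes patients in the Full Analysis Population "who complete the study, without any significant protocol violations". SAP 3.1 takes those who "complete the 52-week treatment period of the study without any significant protocol deviations", and then notes that "the variable to determine a patient completing the 52-week treatment period is from the End of Study eCRF page", where the question asked is whether the subject completed the study.

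**The concern.** A reader of an exposure table takes treatment duration to mean time on drug. In a 52-week placebo-controlled trial with a safety objective, that table shows how much exposure the safety findings rest on. If a boy stops drug at Week 13 and returns for Week 52, the SAP rule records a full year of treatment. The error goes one way only: duration can be too long for these boys, never too short. If stopping differs between arms, the overstatement differs too.

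The Per Protocol wording raises a related question. The SAP names completion of the treatment period as the criterion but implements it with completion of the study. A boy who stopped drug and attended Week 52 passes the field without meeting the written criterion.

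**Working it through.** The plan states no figure here to reproduce. The check is a reading of the rules followed by illustrative arithmetic.

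**Step 1: follow one boy through the rules.** Suppose he stops drug at Week 26, stays in the study and attends Week 52.
- SAP 4.9: he has a Week 52 visit and did not leave the study, so the exception does not apply. His duration ends at Week 52.
- If he had an Early Termination visit when he stopped, it still does not set his duration, because the exception requires leaving the study and having no Week 52 visit.
- Protocol 3.3.3.1: the Week 52 assessments are done. He has completed the study, subject to the safety follow-up if he does not enter the extension.
- SAP 3.1: the study-completion field is Yes, so he counts as having completed the 52-week treatment period.
- SAP 4.4 counts treatment completion and study completion separately, so the SAP itself treats them as different things.

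**Step 2: size for one boy.** SAP 5.2 schedules Weeks 26, 39 and 52 at 182, 273 and 364 days; Week 13 is 13 × 7 = 91. The stop days are assumptions. Overstatement = 364 − stop day.
- Week 13: 364 − 91 = 273 days
- Week 26: 364 − 182 = 182 days
- Week 39: 364 − 273 = 91 days

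**Step 3: size for an arm mean.** With 126 boys randomized 2:1, the arms are 126 × 2/3 = 84 and 126 × 1/3 = 42. The shift from one boy is overstatement ÷ arm size.

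| Stop | Edasalonexent (84) | Placebo (42) |
|---|---|---|
| Week 13 | 273/84 = 3.25 days | 273/42 = 6.5 days |
| Week 26 | 182/84 = 2.17 days | 182/42 = 4.33 days |
| Week 39 | 91/84 = 1.08 days | 91/42 = 2.17 days |

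Non-randomized siblings also belong to the Safety Population, which would make these shifts slightly smaller.

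**Step 4: assumed range for the unknown count.** If 5% of an arm stopped at Week 26 and stayed, the mean would be 0.05 × 182 = 9.1 days too long (9.1/364 = 2.5%). At 10% it would be 0.10 × 182 = 18.2 days (5.0%). These shares are assumptions and have no source in the documents.

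**Step 5: would the 80% compliance cut-off remove such boys from Per Protocol?** Assume full intake until the stop, all kits returned, a constant daily capsule count, and planned capsules running to Week 52. Compliance is then 100 × stop day/364.
- Days 91, 182 and 273 give 25%, 50% and 75%, all below 80%.
- The threshold is 0.80 × 364 = 291.2, so a stop from day 292 onward passes (292/364 = 80.2%; 336/364 = 92.3%).

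SAP 3.2 states this cut-off only for accountability information that arrives after lock and unblinding. Whether it also applies before lock is not stated.

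**The case against.** **The group may be small or empty.** A boy who stops drug is asked for an Early Termination visit, and the Schedule of Assessments has one shared column for Week 52 and early termination, with no separate off-drug schedule. The documents do not show that any boy stopped and then attended Week 52. This stands as a limit on size. It does not remove the case from the design: SAP 4.10 censors observations made after treatment is stopped, and Protocol 9.16.1 plans sensitivity analyses that include them. Both presuppose that such observations can exist.

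**Duration feeds nothing else.** Adverse events are summarized by patient incidence, and the four-week prevalence denominators in SAP 4.13.1 use presence in the study. Treatment discontinuation is counted and listed under SAP 4.4, so stopping is not hidden. This stands.

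**The Per Protocol part is mostly wording.** The field is named, so programming is unambiguous, and it matches the protocol's definition. The SAP phrase could also be read as the study phase rather than as time on drug. Deviation review before unblinding can remove such a boy. Much of this stands; what remains is that the SAP's criterion and its field do not say the same thing.

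**Stronger readings that a reader might infer.**
- That Per Protocol efficacy results would include off-drug data. They would not: SAP 4.10.4(a) reruns the SAP 4.10.1 model, which censors observations after treatment discontinuation.
- That the compliance tables are wrong as well. No separate error is shown. On the Step 5 assumptions an early stopper's compliance falls, as it should.
- That counting certain unreturned kits as 90 used units is an error. SAP 4.9 explains the site convention behind it; it is a prespecified rule, and wanting another bound is a preference.

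**Conclusion.** The duration rule is wrong as written for a boy who stops drug and stays in the study, and no other section corrects it. It overstates his time on drug by 364 days minus his stop day: 273, 182 or 91 days in the three examples. The shift in an arm mean depends on a count that the documents do not give. It is 1.1 to 6.5 days per boy across those examples and the two arm sizes.

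The Per Protocol mismatch is real but secondary. At most it affects who belongs to a sensitivity population, and deviation review or a compliance cut-off may already remove some of these boys.

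The primary and secondary analyses in the Full Analysis Population are unaffected. The documents do not support a claim of biased efficacy results or concealed discontinuation.

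**What to change.** 1. In SAP 4.9, end treatment duration at the date of last dose. SAP 4.13.8 already names a last-exposure date in the analysis data, but the documents do not say how it is derived. Confirm that it is the actual last dose and does not itself default to a visit. If it cannot be confirmed, use the recorded treatment-stop date, which the censoring rule in SAP 4.10 and 4.10.1 already needs.

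2. In SAP 3.1, make the Per Protocol criterion and its field agree, before unblinding. Either take treatment completion from the disposition data planned in SAP 4.4 and list this in SAP section 6 as a change from the protocol, or restore the protocol's study-completion wording and keep the present field.

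The cost is a few lines of SAP text, minor programming and one check of a derivation. Under the first option in item 2, the Per Protocol Population may lose boys who stopped drug but attended Week 52. The second option leaves membership as it is now programmed.

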4.10. Efficacy Evaluation

The FAP is used as the primary population, and the PP and Randomized Populations will be used for sensitivity analyses as described for each efficacy analysis below.

Efficacy endpoints will be listed by patient, and summarized by treatment group and time point, as applicable. For the timed function tests, both the times to complete (seconds) and their speed (i.e. the reciprocals) will be tabulated. In the case of the 10MWT, units will be 10 meters per second. In the case of the stand from supine and the 4-stair climb, units will be task per second. Descriptive statistics will be calculated for quantitative efficacy data as well as for the CFB, and differences between treatment groups as applicable.

Summary statistics for the primary and secondary efficacy endpoints will be presented by investigative site and overall.

If a patient initiates corticosteroid therapy or discontinues study treatment, all observations from that patient after these events will be censored from the efficacy analyses.

4.10.1. Primary Efficacy Analysis

The primary efficacy endpoint is the CFB in the NSAA Total Score at Week 52. NSAA Total Scores and the CFB values will be summarized by treatment group and time point using descriptive statistics.

If a patient initiates corticosteroid therapy or discontinues study treatment, all observations from that patient after these events will be censored from the primary efficacy analyses.

The primary efficacy endpoint analysis will be an MMRM ANCOVA. The MMRM model will include:

- CFB in the NSAA Total Score as the dependent variable
- Variables in the Model

Visit (a categorical variable)	
Treatment (edasalonexent or placebo)	Treatment \times Visit
Region (North America vs. Europe/Asia/Australia)	Region \times Visit
Baseline age (as a continuous variable),	Baseline Age \times Visit
Baseline time to stand from supine (as a continuous variable)	Baseline time to Stand \times Visit
Baseline NSAA score (as a continuous variable)	Baseline NSAA score \times Visit

- Patient as a random effect.

The primary efficacy analysis will test the difference between the edasalonexent versus placebo at Week 52 using this MMRM model.

Sample SAS code for the primary efficacy analysis is provided in [APPENDIX 1: Sample MMRM Code](#).

Descriptive summary statistics including number of patients, mean, standard error, least-square means (LS means), LS means differences, along with the p-values and corresponding 95% CIs

will be provided. Specifically, the primary efficacy endpoint hypothesis test of no treatment difference between edasalonexent and placebo is based on the least-squares means (LS-means) difference and corresponding p-value from the Week 52 visit. The results for the treatment difference for the other visits will also be provided to assess the consistency of treatment effect over different visits.

The repeated-measures analysis will be based on the restricted maximum likelihood method assuming an unstructured covariance structure to model the within-patient errors. A Kenward-Roger approximation will be used for the denominator degrees of freedom. If there is a convergence problem due to the unstructured covariance matrix, a compound symmetry covariance structure will be used to model the within-patient variance; if the compound symmetric covariance structure fails to converge, a variance components approach will be applied.

The primary efficacy endpoint analysis is an observed case analysis, with no imputation of missing data.

Descriptive summary statistics will be provided for each of the 17 NSAA items at each of the scheduled assessment timepoints.

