There is no cure for DMD and those drug treatments that have recently been approved for the disease, i.e., ataluren, which received conditional approval in the European Union, and eteplirsen (Exondys51™), which received accelerated approval in the United States, demonstrate limited efficacy and are appropriate for only a subset of patients. Current standard of care guidelines include the administration of glucocorticoids (Birnkranz, 2018a; Birnkranz, 2018b), which can delay the time to respirator dependence and the onset of scoliosis, and improve performance on measures of clinical function in patients with DMD (Manzur, 2009). However, they do not fully ameliorate symptoms or halt disease progression. Moreover, their use is often limited by numerous side effects, including growth inhibition, delay of pubertal changes, weight gain, behavioral changes, osteoporosis resulting in fractures, Cushingoid facies and habitus, cataracts, and myopathy, a particularly serious concern for patients with DMD (Manzur, 2009; Schakman, 2009; Hanaoka, 2012).

Thus, even though there are a handful of treatment options available, those options are inadequate and a significant need remains for safer and more effective treatments for patients affected by this fatal disease.

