**Table 2: Prohibited Prior and Concomitant Medications**

Medication	Prohibited within 24 weeks prior to Day 1	Prohibited within 4 weeks prior to Day 1 a	Initiation prohibited throughout the study
Corticosteroids b	X	X	X
Deflazacort (Emflaza™)	X	X	X
Ataluren (Translarna™)		X	X
Idebenone (Raxone®)		X	X
Other investigational drugs		X	X
Immunosuppressive therapy		X	X
Warfarin, phenytoin, S mephenytoin, cyclosporine, dihydroergotamine, ergotamine, fentanyl, alfentanil, pimizide, quinidine, sirolimus, tacrolimus, paclitaxel		X	X
Eteplirsen (Exondys 51™) c			X

a If 5 half-lives of the drug is >4 weeks, drug is prohibited for 5 half-lives prior to Day 1.

b Use of inhaled, intranasal, and topical corticosteroids is permitted.

c Use of eteplirsen is permitted if on a stable dose for at least 24 weeks prior to Day 1.

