#### **9.16. Other Statistical Issues**

##### **9.16.1. Missing or Invalid Data**

For the primary and secondary efficacy analyses, the MMRM analyses will be observed case analyses. Multiple imputation will be used as a sensitivity analysis to address missing data (see [Section 9.10.4](#)); additional methods will be specified in the SAP.

If a patient is not able to complete a TFT, a value of 0 tasks/second will be assigned.

If a patient initiates corticosteroid therapy or discontinues study treatment, all observations from a patient after these events will be censored from the primary and secondary efficacy analyses. Sensitivity analyses which incorporate these observations will be defined in the SAP.

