2.5.1. Primary Objective Estimand

The estimand corresponding to the primary objective for this study is shown in [Table 2](#).

Table 2: Estimand for the Primary Objective

Objective	Efficacy of edasalonexent - NSAA Total Score
Estimand	The expected effect in patients if all patients had adhered to the treatment regimen and did not take any corticosteroid therapy or discontinue treatment.
Population	Full Analysis Population (FAP)
Variable	Change from baseline at Week 52 on NSAA Total Score
Intercurrent Events	Treatment discontinuation or initiating corticosteroid therapy or any approved Duchenne therapy : The study is interested in the treatment effect assuming that patients remained on their treatment regimen throughout the study, without initiating corticosteroid therapy or any approved Duchenne therapy.
Population-level Summary	The population summary for the primary estimand is the mean difference in the Week 52 change from baseline on the North Star Ambulatory Assessment Total Score between the edasalonexent and the placebo treatment groups using the model described in Section 4.10.1 . This summary is computed using the FAP as defined in Section 3.1

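### The estimand tables exclude the effect of starting any approved Duchenne therapy, but the censoring rule does not, so later scores of such boys stay in the primary and secondary analyses

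*SAP*

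**What the plan says.** SAP 2.5.1, Table 2, and all three blocks of Table 3 in SAP 2.5.2 name three intercurrent events: stopping study treatment, starting corticosteroids, and starting any approved Duchenne therapy. All are handled the same way. The target is the effect had patients stayed on their regimen "without initiating corticosteroid therapy or any approved Duchenne therapy", which is a hypothetical strategy in substance. The Estimand row of Table 2 is shorter: it speaks of patients who "did not take any corticosteroid therapy or discontinue treatment" and does not mention approved Duchenne therapy.

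The analysis rule is in SAP 4.10.1: "If a patient initiates corticosteroid therapy or discontinues study treatment, all observations from that patient after these events will be censored". SAP 4.10 gives the same two triggers for efficacy in general ("all observations from that patient after these events will be censored from the efficacy analyses"), and protocol 9.16.1 does so for the primary and secondary analyses. SAP 4.10.2 applies the primary method to the three timed function tests. Protocol 9.16.1 also promises analyses that use the censored data: "Sensitivity analyses which incorporate these observations will be defined in the SAP".

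Protocol Table 2 lists ataluren and eteplirsen, among others, under "Initiation prohibited throughout the study". It allows eteplirsen only for boys on a stable dose for at least 24 weeks before Day 1.

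**The concern.** Under a hypothetical strategy, scores recorded after the event do not inform the target, and the plan's way of removing them is censoring. Here the target has three events and the censoring rule has two. Followed as written, the primary test keeps scores that the intercurrent-event rows say should not count. The same applies to all three secondary tests.

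The direction of any bias is unknown. More starters on placebo would shrink the observed difference. More starters on edasalonexent would move it in favour of the drug. With about 34 evaluable boys on placebo, two or three cases would be enough to raise the question of what the primary result estimates.

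**Working it through.** **Text check: does anything else remove these scores?**

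| Place | What it does | Does it close the gap? |
|---|---|---|
| SAP 4.10, SAP 4.10.1, protocol 9.16.1 | Censor after starting corticosteroids or stopping study treatment | No; the third event is absent |
| SAP 3.1, Full Analysis Population | Drops boys on eteplirsen at randomization | No; later starts are not covered |
| Protocol Table 2 | Prohibits starting the drugs | No; no data-handling consequence is given |
| Protocol 5.2.5 | Lists "The patient is unable to comply with the requirements of the protocol" among reasons that may justify stopping treatment | No; stopping is discretionary, so a start need not trigger censoring |
| SAP 3.2 | A significant deviation may remove a boy from the Per Protocol Population | Not for the primary or secondary analyses |
| SAP 4.10.4 (a) to (g), applied to secondaries by 4.10.5 | Sensitivity analyses | No; none adds the event, and none says it uses post-event data |
| SAP 4.10.6 | Multiple imputation | No; it fills missing values, and an uncensored score is not missing |
| SAP 4.13.8 | Lists and tabulates medications | No |
| SAP section 6 | Changes from the protocol | No; silent on this |

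The gap concerns non-steroid therapies only. Deflazacort, for example, is a corticosteroid and already triggers the rule. The sample model code in SAP Appendix 1 is not in the text supplied and could not be checked.

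**Size: inputs from SAP 4.1.** N = 126, allocation 2:1, difference 3.0, SD 4.8, dropout 20%, two-sided level 0.05.

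- Effect size: 3.0 / 4.8 = 0.625, as stated.
- Evaluable: 126 × 0.8 = 100.8, taken as 67 on edasalonexent and 34 on placebo.
- Standard error: 4.8 × √(1/67 + 1/34) = 1.011.
- Base power, two-sample t test: 83.6%, against the stated approximately 80%. The plan is slightly conservative here, which does not affect this point.

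**Assumed inputs.** The documents give neither the share of boys who start such a therapy nor the gain from it. Let the share starting differ between arms by *f*, and let each starter gain *g* NSAA points by Week 52. Keeping these scores shifts the difference by *f* × *g*.

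Excess of starters on placebo:

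| *f* | *g* | Shift | Difference | Power |
|---|---|---|---|---|
| 0 | any | 0 | 3.00 | 83.6% |
| 0.02 | 1 | 0.02 | 2.98 | 83.1% |
| 0.05 | 1 | 0.05 | 2.95 | 82.4% |
| 0.05 | 2 | 0.10 | 2.90 | 81.1% |
| 0.05 | 3 | 0.15 | 2.85 | 79.7% |

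A 5-point excess is about 2 boys of 42 randomized to placebo (0.05 × 42 = 2.1).

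Excess of starters on edasalonexent, with no true drug effect:

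| Shift | Chance of a significant result favouring the drug | Two-sided rejection |
|---|---|---|
| 0 | 2.5% | 5.0% |
| 0.05 | 2.8% | 5.03% |
| 0.10 | 3.1% | 5.1% |
| 0.15 | 3.5% | 5.25% |

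An extreme case, a 10-point excess with a 3-point gain (shift 0.30), gives 6.0% two-sided rejection. All these figures credit the full gain at Week 52 whatever the start date, so each is an upper value for its case.

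**The case against.** The strongest reply is that this is a small wording mismatch. Starting these drugs is prohibited, and the protocol's introduction says the approved drugs "demonstrate limited efficacy and are appropriate for only a subset of patients". A 3-point gain equals the whole planned edasalonexent effect, so the top of the assumed range is unlikely. That stands, and it is why the effect is called probably small.

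SAP 3.2 also has a deviation category for restricted concomitant medication changes. Significant deviations are reviewed before unblinding, and the Per Protocol analysis is run on the primary and secondary endpoints. This is a real partial safeguard. But exclusion is at the sponsor's discretion, it removes the whole patient rather than the scores after the event, and it is a sensitivity analysis that does not implement the stated estimand.

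The Estimand row of Table 2 may be read as an incomplete summary rather than a contradiction. It is also fair that SAP 4.10 and 4.10.1 give a programmer one instruction. Both are reasonable readings, but neither removes the mismatch: the instruction does not produce what the intercurrent-event rows describe.

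Finally, censoring has a cost. Dropping the two placebo boys in the 5-point example (67 and 32 boys, difference 3.0) gives 82.1% power by the same t test, against 82.4% for keeping them at a 1-point gain. The repeated-measures model would recover some of that loss from earlier visits. So power does not decide the matter; agreement between the estimand and the analysis does.

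**Conclusion.** The concern holds. The plan defines its primary and secondary targets as the effect without starting any approved Duchenne therapy, then analyses the data without removing scores recorded after such a start. The fault is certain from the text. Its numerical size is an estimate that depends on assumed uptake and gain. For a 5-point imbalance and gains of 1 to 3 points, the planned difference moves by 0.05 to 0.15 points, which costs about 1 to 4 percentage points of power. If the imbalance runs the other way, the one-sided error rises by 0.3 to 1.0 percentage points. Equal uptake in both arms, with equal gain, leaves the difference unchanged.

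It should be fixed before unblinding. If the mismatch is noticed only afterwards, either reading can be defended from the SAP, and the choice could follow the results.

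**What to change.** Choose one of two repairs before unblinding.

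1. **Extend the rule.** Add to the censoring sentences in SAP 4.10 and 4.10.1 a third trigger: starting any approved Duchenne therapy, from a named list, by recorded start date after first dose. SAP 4.10.2 inherits it. Dating the trigger after first dose avoids censoring from Day 1 the boys already on eteplirsen who enter sensitivity analysis 4.10.4(b). Add the event to the Estimand row of Table 2, and record the difference from protocol 9.16.1 in SAP section 6.
2. **Narrow the estimand.** Remove the event from the intercurrent-event rows of Tables 2 and 3, and state that later scores are used as observed.

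In either case, name at least one sensitivity analysis that includes post-event observations, as protocol 9.16.1 promises. It would also help to state that corticosteroid therapy in the rule does not mean the inhaled, intranasal and topical use that the protocol permits.

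The first repair costs one phrase in two sentences, one table row, one line in section 6, and one flag built from the concomitant-medication start dates already collected under protocol 6.4.5. Its downside is that a few more observations are censored.
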